## 2.0 **STUDY OBJECTIVES**

### 2.1 **Primary Objectives**

**2.1.1** To compare changes in pre- to post-chemotherapy cognitive function, as measured by DMS score, in our cohort of patients with breast cancer receiving memantine to historical controls.

### 2.2 **Secondary Objectives**

**2.2.1** To compare pre- to post-chemotherapy changes in all other objective and self-reported cognitive function measures.

**2.2.2** To examine associations between objective and self-reported cognitive function with depression, anxiety, fatigue, menopausal status, baseline IQ, and perceived cognitive effort, cross-sectionally pre- and post-chemotherapy.

**2.2.3** To explore the impact of cognitive decline on health-related quality of life (HRQOL), functional status, depression, and anxiety.

**2.2.4** To estimate the feasibility of conducting a clinical trial of memantine for attenuating cognitive decline in patients with breast cancer during chemotherapy.

**2.2.5** To describe the safety of administering memantine to patients with breast cancer during chemotherapy.

### 2.3 **Exploratory Objectives**

**2.3.1** To compare pre- to 6 months post-chemotherapy changes in objective and self-reported cognitive function measures.

**2.3.2** To describe changes in depression, anxiety, fatigue, HRQOL, and functional status from pre- to 6 months post-chemotherapy.

## 3.0 **Criteria for Evaluation / Study Endpoints**

### 3.1 **Primary Endpoint**

The primary endpoint is change in the pre- to post-chemotherapy DMS score. The DMS will be quantified as percent correct at 12-second delay.

### **3.2 Secondary Endpoints**

**3.2.1** Changes in other objective (HVLT-R, RVP, OTS, Digit Span, COWA, Animal Naming Test) and self-reported (PROMIS Cognitive Function) cognitive measures will be measured from pre- to post-chemotherapy.

**3.2.2** Depression (PROMIS-Depression), Anxiety (PROMIS-Anxiety), fatigue (Functional Assessment of Chronic Illness Therapy – Fatigue, FACIT-F), menopausal status (Hormonal Status Questionnaire and follicle stimulating hormone level, FSH), and perceived cognitive effort (NASA-Task Load Index, NASA-TLX) will be measured pre- and post-chemotherapy. Baseline IQ (Wechsler Adult Test of Reading, WTAR) will be measured pre-chemotherapy only.

**3.2.3** Health-related quality of life (Functional Assessment of Cancer Therapy – General, FACT-G) and functional status (Patient-reported Karnofsky Performance Status, Patient-KPS) will be measured pre- and post-chemotherapy.

**3.2.4** Recruitment will be measured as proportion of approached participants who agree to enroll and number of participants enrolled per month. Retention will be measured as proportion of enrolled participants who complete the primary outcome measure pre- and post-chemotherapy. Adherence will be measured as patient-reported proportion of prescribed doses of memantine actually taken.

**3.2.5** Safety will be measured as the frequency of reported adverse events (AEs).

### **3.3 Exploratory Endpoints**

**3.3.1** Changes in the DMS, HVLT-R, RVP, OTS, Digit Span, COWA, Animal Naming Test, and PROMIS Cognitive function will be measured from pre- to 6 months post-chemotherapy in a subset of participants who volunteer for extended longitudinal observation.

**3.3.2** Changes in PROMIS-Depression, PROMIS-Anxiety, FACIT-F, FACT-G, and Patient-KPS will be measured from pre- to 6 months post-chemotherapy in a subset of participants who volunteer for extended longitudinal observation.

## **4.0 PATIENT ELIGIBILITY**

In order to participate in this study a participant must meet ALL of the eligibility criteria outlined below.

### **4.1 Inclusion Criteria**

Eligible participants must meet all of the following criteria to be enrolled in the study:

**4.1.1** Able to provide informed consent

**4.1.2** At least 18 years of age

- 4.1.3 Able to speak English
- 4.1.4 Diagnosed with breast cancer, Stages I – III
- 4.1.5 Scheduled for adjuvant or neoadjuvant chemotherapy

#### 4.2 Exclusion Criteria

[figure not shown]
Eligible participants must not have any of the following to be enrolled in the study:

- 4.2.1 A history of adverse reaction to memantine
- 4.2.2 Another cancer diagnosis with an estimated survival of less than five years
- 4.2.3 Previous chemotherapy exposure
- 4.2.4 Severe cognitive impairment, defined as Blessed Orientation Memory Concentration Test (BOMC)  $\geq 11$ .
- 4.2.5 Pregnancy, confirmed by a negative pregnancy test within 30 days of study enrollment, or breastfeeding
- 4.2.6 Current alcohol or drug abuse

### 5.0 TREATMENT PLAN

#### 5.1 Schema

Figure 1: One arm phase II study evaluating the feasibility and efficacy of using memantine to prevent cognitive decline during adjuvant or neoadjuvant chemotherapy in patients with breast cancer

a. Objective: DMS, HVLT-R, RVP, OTS, Digit Span, COWA, ANT, BOMC, WTAR; Subjective: PROMIS Cognitive Function

b. NASA-TLX, PROMIS Depression, PROMIS Anxiety, PROMIS Sleep Disturbance, FACIT-F, KPS, FACT-G, Hormonal Status

c. Follicle-stimulating hormone level

d. TC: q3wk x 4 cycles; AC-T: q2wk x 4 cycles + taxol x 12 wk; TCH: q3wk x 6 cycles (anti-HER-2 therapy will continue beyond this point)

e. Modified Brief Medication Questionnaire-Specific

#### 5.2 Treatment Dosage and Administration

Participants will receive memantine beginning within four weeks prior to and one week after chemotherapy initiation. All patients will be gradually titrated to 10 mg twice daily as follows: 5 mg daily in week 1, 5 mg twice daily in week 2, 5 mg each morning and 10 mg each evening in week 3, then 10 mg twice daily in week 4. Participants will continue 10 mg twice daily until 4 weeks (range: 2 to 12

weeks) after the last dose of chemotherapy. Depending on the chemotherapy regimen, total duration will range from approximately 12-30 weeks.

| REGIMEN DESCRIPTION |       |                                       |                                     |
|---------------------|-------|---------------------------------------|-------------------------------------|
| Agent               | Route | Dose                                  | Schedule                            |
| Memantine HCl       | Oral  | 5 mg daily                            | Week 1                              |
|                     |       | 5 mg twice daily                      | Week 2                              |
|                     |       | 5 mg each morning, 10 mg each evening | Week 3                              |
|                     |       | 10 mg twice daily                     | Week 4 to 4 weeks post-chemotherapy |

### Prescribing Information

Full prescribing information for memantine can be found at the following web address:

[https://www.accessdata.fda.gov/drugsatfda\\_docs/label/2013/021487s010s012s014\\_021627s008lbl.pdf](https://www.accessdata.fda.gov/drugsatfda_docs/label/2013/021487s010s012s014_021627s008lbl.pdf)

### 5.3 Toxicities and Dosing Delays

Any patient who receives treatment on this protocol will be evaluated by the CRA, PI, or Co-Is for toxicity. Patients will be assessed at least weekly during the titration of memantine and no less frequent than every three weeks during systemic chemotherapy. For patients receiving anti-HER2 directed therapy in addition to chemotherapy, toxicity will only be assessed during the chemotherapy segment of the regimen.

Toxicity will be assessed according to the NCI Common Toxicity Criteria for Adverse Events (CTCAE), version 5.0.

In assessing adverse events (AEs) and attribution during the course of this study, we will consider those AEs commonly associated with memantine, the specific chemotherapy administered, and chemotherapy-associated medications received.

Though all patient-reported symptoms will be recorded and examined for their association with memantine, the following most common side effects of memantine will be explicitly solicited from participants by the study team: headache, dizziness, confusion, constipation, diarrhea, and fatigue. See section 6.1.7 for additional information on memantine warnings and precautions. Differentiation between memantine-associated toxicities and toxicities attributable to alternative agents will be guided by Assessing of Causality of Adverse Events outlined in 8.1.2. The treating provider will be notified of any possible, probable, or definite AEs and involved in decisions to continue, dose reduce, or stop memantine. At any time, the participant may decide to dose reduce or discontinue memantine.

If a participant experiences a grade 1 toxicity with a probable or definite attribution to memantine, the participant will remain on the same dose and symptoms will be monitored daily until the side effect is resolved.

If a participant experiences a grade 2 toxicity with a probable or definite attribution to memantine, the dose will be reduced to 5 mg PO BID (or the last tolerated dose if less) and symptoms will be monitored daily until the side effect is resolved. If no improvement, memantine will be discontinued.

If a participant experiences a grade 3 toxicity with a probable or definite attribution to memantine, the participant will discontinue memantine.

If a participant experiences toxicity with a possible attribution to memantine, the participant will remain on the same dose of memantine and symptoms will be monitored weekly until the side effect is resolved.

If a participant experiences toxicity with an unlikely or unrelated attribution to memantine, the participant will remain on the same dose and side effects will be monitored according to the scheduled outlined in the protocol (i.e., weekly during titration or no less than every 3 weeks during maintenance).

Regardless of grade or relationship with memantine, if one of the memantine side effects listed below is the reason for dose reduction of chemotherapy, the participant will reduce memantine to 5 mg PO BID (or the last tolerated dose if less) and symptoms will be monitored daily until the side effect is resolved. If no improvement, memantine will be discontinued.

- Headache
- Dizziness
- Confusion
- Constipation
- Diarrhea
- Fatigue

Regardless of whether the participant experiences any AEs, if creatinine clearance falls below 30 mL/min, the dose will also be decreased to 5 mg PO BID. If creatinine clearance falls below 5 mL/min, the study medication will be stopped.

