### 6.1.7 Adverse Events Associated with Commercial Drug

In a meta-analysis of six phase III placebo-controlled trials of 959 patients receiving memantine HCl for moderate to severe Alzheimer's disease, the most frequently identified side effects were dizziness (6.3%), headache (5.2%), constipation (4.6%), and somnolence (3.4%). The following have also been reported with the following frequencies: confusion (6%), hypertension (4%), coughing (4%), pain (3%), hallucination (3%), vomiting (3%), dyspnea (2%), and fatigue (2%). A comprehensive list of adverse effects can be found at the following web address:

[https://www.accessdata.fda.gov/drugsatfda\\_docs/label/2013/021487s010s012s014\\_021627s008lbl.pdf](https://www.accessdata.fda.gov/drugsatfda_docs/label/2013/021487s010s012s014_021627s008lbl.pdf)

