#### **7.10 Assessment of Safety**

Any patient who receives at least one dose of study therapy on this protocol will be evaluable for toxicity. Each patient will be assessed at least weekly during the titration of memantine and no less frequent than every three weeks during systemic chemotherapy for the development of any toxicity according to the Time and Events table. Toxicity will be assessed according to the NCI CTCAE version 5.

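### Section 5.3 does not prompt for somnolence at adverse-event contacts, although 6.1.7 places it among memantine's four most frequent effects; adding it would be a cheap gain in safety ascertainment

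*Combined protocol and SAP*

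**What the plan says.** Section 5.3 sets out two routes by which symptoms reach the adverse-event record. The first is general: "all patient-reported symptoms will be recorded and examined for their association with memantine". The second is prompting: "the following most common side effects of memantine will be explicitly solicited from participants by the study team: headache, dizziness, confusion, constipation, diarrhea", followed by fatigue as the sixth and last item. The list cites reference 64, the prescribing information. The next sentence reads "See section 6.1.7 for additional information on memantine warnings and precautions".

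Section 6.1.7 gives rates from two sources. From reference 85, a meta-analysis in moderate to severe Alzheimer's disease: "the most frequently identified side effects were dizziness (6.3%), headache (5.2%), constipation (4.6%), and somnolence (3.4" (the last figure is 3.4%). From reference 64: "confusion (6%), hypertension (4%), coughing (4%), pain (3%), hallucination (3%), vomiting (3%), dyspnea (2%), and fatigue (2" (the last figure is 2%).

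The same six symptoms appear again later in 5.3 as a trigger list. Memantine is reduced "if one of the memantine side effects listed below is the reason for dose reduction of chemotherapy".

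Section 7.10 states "Any patient who receives at least one dose of study therapy on this protocol will be evaluable for toxicity" and has patients assessed "for the development of any toxicity according to the Time and Events table". Contacts are at least weekly in titration and at least every three weeks during chemotherapy. Section 3.2.5 defines the safety endpoint by how often adverse events are reported. Section 9.3 plans one tabulation of all events and does not separate prompted from volunteered ones.

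**The concern.** The safety endpoint counts what is reported, so it depends on what is asked. Staff must raise six symptoms at every toxicity contact; anything else depends on the participant mentioning it or on general questioning. Section 5.3 describes its list as the most common effects, yet one of the four effects that 6.1.7 ranks highest is left out, while an effect with a lower quoted rate is included.

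At stake is the comparability of rows in the adverse-event table. If somnolence is recorded less completely than headache, dizziness or fatigue, its row could look low for reasons of ascertainment alone. Section 9.2 says the trial is to provide preliminary data for a larger placebo-controlled study, so a fair description of tolerability has some value beyond this trial.

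**Working it through.** The plan gives no figure on this point to reproduce. The check is a comparison of lists, followed by a calculation of scale.

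**1. The two sections side by side.** Rates and references are from 6.1.7, and the prompt column is from 5.3. Expected count = 56 × rate. The 56 is the planned enrolment in 9.2; using it assumes that everyone enrolled takes at least one dose.

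| Effect | Rate in 6.1.7 | Reference | Prompted in 5.3 | Expected in 56 |
|---|---|---|---|---|
| Dizziness | 6.3% | 85 | yes | 3.53 |
| Headache | 5.2% | 85 | yes | 2.91 |
| Constipation | 4.6% | 85 | yes | 2.58 |
| **Somnolence** | **3.4%** | **85** | **no** | **1.90** |
| Confusion | 6% | 64 | yes | 3.36 |
| Hypertension | 4% | 64 | no | 2.24 |
| Coughing | 4% | 64 | no | 2.24 |
| Pain | 3% | 64 | no | 1.68 |
| Hallucination | 3% | 64 | no | 1.68 |
| Vomiting | 3% | 64 | no | 1.68 |
| Dyspnea | 2% | 64 | no | 1.12 |
| Fatigue | 2% | 64 | yes | 1.12 |
| Diarrhea | not given | – | yes | – |

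Three of the four leading meta-analysis effects are prompted, and somnolence is the exception. Diarrhea is prompted but has no rate in 6.1.7, so 6.1.7 cannot be the whole basis of the list.

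**2. Scale if the rate carried over.** Expected somnolence events: 56 × 0.034 = 1.90. Chance of at least one: 1 − (1 − 0.034)^56 = 0.856. At half the rate (1.7%) the expected count is 0.95 and the chance is 1 − 0.983^56 = 0.617. At double the rate (6.8%) they are 3.81 and 1 − 0.932^56 = 0.981.

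**3. Effect of not prompting.** The documents give no figure for the share of cases that participants would volunteer. Taking 25% to 75% as an assumption:

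- At 75%: 1.43 expected recorded events, with a chance of at least one of 1 − (1 − 0.0255)^56 = 0.765.
- At 25%: 0.48 expected recorded events, with a chance of at least one of 1 − (1 − 0.0085)^56 = 0.380.
- At 100%: nothing is lost.

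The lower end shows that a term with a true count near two could drop out of the table. The upper end shows that there may be no loss.

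**4. Other places where sleepiness is asked about.** FACIT-F item 9 (Appendix L) asks about needing to sleep in the daytime. The schedule in 7.1 places FACIT-F at baseline, post-chemotherapy and, for the subset, six months. Under 7.3 memantine runs until the post-chemotherapy assessment, so the item is asked once at about the end of treatment. It is not part of adverse-event collection and is not asked in titration or between chemotherapy cycles.

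**The case against.** The strongest reply is that the two lists have different sources. The prompt list cites the prescribing information, and the 3.4% comes from the meta-analysis. Whether the six items are the leading effects in the prescribing information cannot be checked here. A reader might infer that 5.3 and 6.1.7 contradict each other, but the documents do not support that. What remains is narrower: both are the protocol's own sources, 5.3 points to 6.1.7, and 6.1.7 ranks somnolence fourth in the meta-analysis.

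The second reply is that capture is already broad. Volunteered symptoms are recorded, any toxicity is assessed under CTCAE v5.0, the fatigue and confusion prompts are close neighbours, and FACIT-F item 9 asks about daytime sleep. All of this stands, and it is why the under-count may be zero. It does not remove the difference between symptoms that must be asked about and one that need not be.

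Third, a reader might infer that hallucination (3%) should be added on the same argument. It should not. Hypertension and coughing (4% each) are more frequent, pain and vomiting (3% each) are as frequent, and none of them is prompted. Singling out hallucination as a central nervous system effect is a judgement that the protocol does not make.

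Fourth, a reader might infer that the dose rules leave somnolence uncovered. The grade-based rules in 5.3 apply to any toxicity attributed to memantine, not only to the six listed.

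Finally, the version in hand is Amendment 10, dated 4/23/21. Amendment 1 was dated 8/26/19, and 9.2 expected recruitment within one year. Accrual status is not given. A change now helps only later contacts, so the 56-participant figures overstate what it could recover.

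**Conclusion.** The point holds as a modest improvement to safety ascertainment; it is not an error in the plan. Somnolence is the one effect among the four leading meta-analysis effects that no adverse-event contact requires staff to ask about, and it may therefore be recorded less completely than the six prompted effects.

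The size of any under-count cannot be found from the documents. The 1.9 expected events should not be read as 1.9 missed events. That figure also rests on carrying a rate over from moderate to severe Alzheimer's disease to a trial that excludes severe cognitive impairment (BOMC of 11 or more), with no placebo rate given in 6.1.7.

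Only the descriptive safety objective (2.2.5) is affected. The primary DMS analysis, the sample size and the power are untouched, and no planned test compares adverse-event terms.

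**What to change.** In 5.3, add somnolence to the symptoms that staff raise at each existing toxicity contact. Leave the six-item chemotherapy-dose-reduction trigger list and every dose rule unchanged, and state that the solicited list and the trigger list now differ on purpose.

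In 9.3, tabulate solicited and spontaneously reported adverse events separately. Count somnolence as spontaneous for contacts made before the change.

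The cost is one more question at contacts that already take place and one split in a table. There are two downsides. More low-grade somnolence caused by chemotherapy or supportive drugs will be recorded, and it is hard to attribute without a control arm; the log of CNS-active medications in 7.6, which covers anxiolytics and antihistamines, helps. Ascertainment of one term also changes mid-trial, which is why the table should keep earlier contacts apart. If the sponsor prefers to leave somnolence out, a sentence in 5.3 giving the reason would be enough.

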### **5.5 Duration of Therapy**

Treatment will continue until 4 weeks (range 2-12 weeks) after the last dose of systemic chemotherapy or until:

- Unacceptable adverse event(s)
- Inter-current illness that prevents further administration of treatment, **OR**
- Participant decides to withdraw from the study

Decisions to remove a participant from the trial or discontinuation of treatment before planned study completion will be undertaken in conjunction with consultation from the study PI.

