### **5.7 Study Withdrawal**

Participants will be removed from protocol therapy and the PI notified when any of the criteria listed in section 5.5 apply. The reason for discontinuation of the protocol therapy will be documented on the eCRF.

If a participant decides to withdraw from the study (and not just from protocol therapy) an effort will be made to complete and report study assessments as thoroughly as possible. At the time of withdrawal, the PI will attempt to establish as completely as possible the reason for the study withdrawal.

- The patient will be asked if they are willing to allow for the abstraction of relevant information from their medical record in order to meet secondary objectives outlined in the protocol.
- The patient will be asked if they are willing to complete the Modified Brief Medication Questionnaire-Specific at the time of study withdrawal.
- If the reason for removal of a participant from the study is an adverse event, the principal specific event will be recorded on the eCRF.

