#### **Assessing Causality of Adverse Events**

The likelihood of causality of all AE's will be graded as described below. Given that potential side effects of memantine overlap with those due to chemotherapy (and many other medications), we will consider not only the presence/absence of the AE, but also worsening in the severity or frequency of the AE in assessing causality.

Unrelated: Adverse event and/or its severity or frequency are clearly due to extraneous causes (e.g., underlying disease, environment)

Unlikely (must have 2): Adverse event and/or its severity or frequency:

1. does not have temporal relationship to intervention
2. could not readily have been produced by the participant's clinical state

3. could have been due to environmental or other interventions
4. does not follow a known pattern of response to intervention
5. does not reappear or worsen with reintroduction of intervention

Possible (must have 2): Adverse event and/or its severity or frequency:

1. has a reasonable temporal relationship to intervention
2. could not readily have been produced by the participant's clinical state
3. could not have been due to environmental or other interventions
4. follows a known pattern of response to intervention

Probable (must have 3): Adverse Event and/or its severity or frequency:

1. has a reasonable temporal relationship to intervention
2. could not readily have been produced by the participant's clinical state or have been due to environmental or other interventions
3. follows a known pattern of response to intervention
4. disappears or decreases with reduction in dose or cessation of intervention

Definite (must have all 4): Adverse Event and/or its severity or frequency:

1. has a reasonable temporal relationship to intervention
2. could not readily have been produced by the participant's clinical state or have been due to environmental or other interventions
3. follows a known pattern of response to intervention
4. disappears or decreases with reduction in dose or cessation of intervention

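### Section 5.3 keeps a 'possible' memantine toxicity on the same dose at any grade, and 8.1.2 caps symptoms that chemotherapy could explain at 'possible' until memantine is lowered

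*Combined protocol and SAP*

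**What the plan says.** Section 5.3 (Toxicities and Dosing Delays) sets dose action by grade when attribution to memantine is probable or definite. Grade 1 stays on dose with daily monitoring. Grade 2 goes down to 5 mg twice daily, or the last tolerated dose if lower, and stops if there is no improvement. For grade 3: "If a participant experiences a grade 3 toxicity with a probable or definite attribution to memantine, the participant will discontinue memantine".

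The next category has a single rule without a grade: "If a participant experiences toxicity with a possible attribution to memantine, the participant will remain on the same dose of memantine", with weekly monitoring until resolution. The lowest categories have similar wording: "If a participant experiences toxicity with an unlikely or unrelated attribution to memantine, the participant will remain on the same dose".

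Other provisions can change the dose:

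- Section 5.3: "The treating provider will be notified of any possible, probable, or definite AEs and involved in decisions to continue, dose reduce, or stop memantine". The participant may also reduce or stop at any time.
- Section 5.3: whatever the grade or attribution, memantine goes down to 5 mg twice daily "if one of the memantine side effects listed below is the reason for dose reduction of chemotherapy". The list has six symptoms, dizziness and confusion among them. A fall in creatinine clearance has its own rule.
- Sections 5.5 and 5.7: an unacceptable adverse event ends treatment, and "Participants will be removed from protocol therapy and the PI notified when any of the criteria listed in section 5.5 apply". 'Unacceptable' is not tied to a grade or an attribution.

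Section 5.2 titrates all patients through 5, 10 and 15 mg/day in weeks 1 to 3 to 20 mg/day from week 4. The start may fall anywhere from four weeks before to one week after the first chemotherapy dose, so titration can overlap chemotherapy.

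**The concern.** The strict rules in 5.3 depend on reaching 'probable'. Section 8.1.2 itself recognises that memantine and chemotherapy share side effects, and for a shared symptom 'probable' is hard to reach while the dose is unchanged. The evidence that would raise the attribution is improvement on a lower dose, but the attribution rules order a lower dose only after the attribution has been raised.

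Dizziness and confusion are among the six effects the protocol solicits as memantine's own. Severe confusion during chemotherapy is a case where staff need a clear instruction, and the written one is to carry on. Section 10.4 requires conduct as written except in emergencies, so the default matters.

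A second gap concerns titration. If 'same dose' means holding the current step, a participant with a 'possible' event stays low. If it means only not reducing, the calendar raises the dose through an unresolved event. Two members of staff could treat the same event in opposite ways, which affects both safety and the dose received.

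**Working it through.** No sample-size or power figure depends on this point, so there is no plan figure to reproduce. The check is a comparison of the rules, an enumeration of the causality criteria, and dose arithmetic.

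**Step 1. The 5.3 rules side by side**

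| Grade | Probable or definite | Possible |
|---|---|---|
| 1 | same dose, daily monitoring | same dose, weekly monitoring |
| 2 | reduce to 5 mg twice daily, daily monitoring, stop if no improvement | same dose, weekly monitoring |
| 3 | stop | same dose, weekly monitoring |

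A grade 1 'probable' headache is watched daily, while a grade 3 'possible' confusion is watched weekly on an unchanged dose.

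**Step 2. What 'probable' needs in 8.1.2**

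The four criteria are: T, a reasonable time relation; A, no ready explanation by clinical state and none by environment or other interventions; K, a known response pattern; D, improvement after the dose is lowered or stopped. 'Probable' needs T + A + K + D of at least 3, and 'definite' needs 4. 'Possible' needs 2 of T, K and the two halves of A counted separately. Taking T = K = 1 and clinical state excluded, the highest category reached is:

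- Chemotherapy could explain it, memantine not lowered: A = 0, D = 0, sum 2. Ceiling 'possible'.
- Chemotherapy could explain it, improvement after lowering: A = 0, D = 1, sum 3. 'Probable'.
- Chemotherapy excluded, memantine not lowered: A = 1, D = 0, sum 3. 'Probable'.
- Chemotherapy excluded, improvement after lowering: sum 4. 'Definite'.

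Running every combination of criteria gives the same ceilings. In the first case the grade 3 stopping rule does not apply, and the 'possible' rule leaves the dose unchanged.

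**Step 3. Where the ceiling does not apply**

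It does not apply to an event before the first chemotherapy dose. It also does not apply where the assessor judges that chemotherapy does not explain the worsening, because 8.1.2 lets severity and frequency be assessed as well as presence.

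**Step 4. Titration during a 'possible' event**

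Take an event that starts in week 1 and is unresolved in week 4. Holding the step gives 5 mg/day. Following the 5.2 calendar gives 20 mg/day, and 20/5 = 4, a fourfold difference from the same sentence.

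**Step 5. Dose arithmetic for the fix**

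Planned dose over 12 weeks: 7 × (5 + 10 + 15) + 9 × 140 = 1,470 mg. Over 30 weeks: 210 + 27 × 140 = 3,990 mg.

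- One maintenance week at 5 mg twice daily instead of 20 mg/day: 140 − 70 = 70 mg lost, 4.8% of 1,470 or 1.8% of 3,990.
- Staying at 5 mg twice daily from week 4 to the end: 9 × 70 = 630 mg (42.9%) or 27 × 70 = 1,890 mg (47.4%).
- A titration step delayed by one week: 140 − 35 = 105 mg at 5 mg/day (7.1%; 2.6%), 140 − 70 = 70 mg at 10 mg/day (4.8%; 1.8%), 140 − 105 = 35 mg at 15 mg/day (2.4%; 0.9%).
- One week fully withheld, then resumed where titration stopped: 140 mg (9.5%; 3.5%).

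**The case against.** The strongest reply is that 5.3 leaves room to act. It involves the treating provider in decisions to reduce or stop for 'possible' events, and it lets the participant reduce. The chemotherapy-reduction trigger ignores attribution and itself supplies the lower dose from which 'probable' can be reached. Sections 5.5 and 5.7 require removal for an unacceptable event, and the monitoring committee sees grade 3 or greater events. Causality is a medical judgement. Keeping participants on drug when chemotherapy is a plausible cause also protects exposure in a single-arm efficacy study.

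Most of this stands, and it rules out three stronger readings:

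- A reader might infer that 5.3 forbids reducing memantine for a 'possible' event. It does not, because reduction is named among the decisions the provider joins.
- A reader might infer that 'probable' can never be reached for a shared symptom. It can, after a reduction made for any reason.
- A reader might infer that unrelated symptoms freeze titration. Section 5.2 titrates all patients, and the rule for unlikely or unrelated events provides for weekly checks while titration is under way, so the better reading is that titration continues. No such wording accompanies the 'possible' rule.

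The default itself is not answered. Apart from the creatinine rule, the only objective trigger waits until a listed symptom has already cost the participant chemotherapy dose. The other routes depend on case-by-case judgement, on the participant, or on an undefined term. Committee review every six to twelve months is too infrequent to settle one participant's dose.

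**Conclusion.** The point holds as a gap in the mandatory dose rules and should be fixed. For a grade 3 'possible' event, the written instruction is the same dose with weekly monitoring. For a symptom or worsening that chemotherapy could readily explain, 'possible' is the highest attribution available until memantine is lowered: at most 2 of the 3 criteria required. For 'possible' events in weeks 1 to 3, the text also leaves open whether the next increase goes ahead.

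This assumes that assessors apply the 8.1.2 criteria as written and judge that chemotherapy could explain the symptom. Section 8.1.2 states the overlap in general terms and does not name dizziness or confusion as shared, so these are illustrations.

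The size of the harm cannot be given. The documents contain no rate of grade 2 or 3 'possible' events and no distribution of memantine start days. The fourfold dose difference describes how far the two readings diverge for one unresolved event, not how often that happens.

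**What to change.** Amend Section 5.3 in two places.

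1. For a grade 3 or higher 'possible' event, reduce memantine to 5 mg twice daily, or the last tolerated dose if lower; withhold it if the participant is already at or below that dose. Monitor daily and re-grade attribution afterwards. Stop if attribution becomes 'probable' or if there is no improvement. This reuses the step already in 5.3 for symptoms that force a chemotherapy reduction.
2. Do not make the next 5 mg titration step while a grade 2 or higher 'possible' event is unresolved. State that titration continues for grade 1 'possible' events and for unlikely or unrelated events.

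The cost is lost memantine exposure in those affected, on the scale shown in Step 5 of the working: a few percent of planned dose per week reduced or delayed, and over 40% if the lower dose is kept from week 4 to the end. Anyone stopped loses all remaining dose. Some of those affected will have symptoms caused by chemotherapy. A few may be stopped because recovery between cycles is mistaken for improvement on the lower dose, or because the symptom does not improve. Longer titration and daily monitoring add some contacts. Full interruption with stepwise re-titration for every grade 3 'possible' event would cost more exposure and is not needed to close the gap.
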